Eligible patient subjects will be identified through our best practice alert build within Epic using similar methodology that has been used in other ongoing studies by the PIs. Upon opening the patient's medical chart and placing orders, the build will examine the patient record, and all patients who meet inclusion and exclusion criteria will automatically be identified and enrolled into the study. The inclusion criteria will be all adults ≥ 18 years who are seen in an internal medicine or cardiology clinic of one of our study sites and who have a left ventricular ejection fraction of $\leq 40\%$ and membership in the Yale Heart Failure Registry (NCT04237701). Our target sample size is 655 subjects per study arm, for a total of 1310 patients. A patient's study arm (whether a patient generates an alert or not) will be determined by the randomization status of the provider at the time of their first eligible outpatient visit.

As this is an intervention assessing the influence of an alert system on provider behaviors surrounding heart failure prognosis, we cannot inform patients of their participation in the study at the time of enrollment, as this would contaminate the randomized exposure. As this study presents minimal risk to patients, we will be requesting a waiver of informed consent at the patient level.

Randomization

Randomization in this study will occur at the level of the provider. All consented physicians will be randomized within Epic to either the intervention group or the control (usual care) group via a permuted block randomization scheme to ensure an equal number of providers in each study arm. Logic checks within the alerts ensure that once a provider is assigned to an arm, they remain in that arm for the remainder of the study. This will create 100 clusters (providers) to which eligible patient participants will be assigned upon their outpatient visit.

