Because it is likely that providers may internalize the best practice metrics once repeatedly exposed to the alert, cluster randomization of patients at the level of the provider will ensure that providers consistently receive an alert or not, which will reduce contamination between study arms. It will also minimize the chance that providers get so accustomed to seeing an alert that they will become less attentive to the condition in patients not generating an alert. We will ask the providers to not discuss the details of the trial and/or alerts amongst each other so as to limit the contamination across study groups. Additional pre- and post- intervention analyses in the control group, leveraging the three-month baseline period, can assess the level of contamination and the effect of secular trends towards better care over time.

Intervention

Providers randomized to the intervention arm will have a best practice alert appear for each of their eligible patients upon opening of the order entry screen in the patient's medical record. This alert informs the provider to the presence of HFrEF, notes the patient's current LVEF and current evidence based medications, and gives access to an order set with recommended evidence- based and FDA- approved therapies for patients with HFrEF. Providers will also have access to a link to best available guideline recommended information regarding treatment of heart failure. With the alerts, we will also make sure to note that monitoring and follow-up are required for prescriptions.

The alert will appear as follows:

Adherence to Evidence Based Therapies in HFrEF

Your patient meets the criteria for having heart failure with reduced Ejection Fraction. Relevant values are listed below:

LVEF

Current Heart Failure Therapies

Beta blocker Carvedilol 3.125mg BID

ACEi/ARB/ARNI Lisinopril 5mg

MRA None

SGLT2-inhibitor None

In order to improve the care of patients with HFrEF, we have included the evidence based medical therapy order set for each of the recommended medications.

OPEN ORDER SET

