 valsartan (DIOVAN)
Disp-30 tablet, R-2

▼ Beta Blockers

▼ Bisoprolol (Zebeta)
FDA-approved for hypertension
 bisoprolol-hydrochlorothiazide (ZIAC) 5-6.25 mg per tablet
Disp-30 tablet, R-2

▼ Carvedilol (Coreg)
FDA-approved to treat hypertension, heart failure with reduced ejection fraction, left ventricular dysfunction following myocardial infarction in clinically stable patients
 carvedilol (COREG)
Disp-60 tablet, R-2

▼ Metoprolol succinate (Toprol-XL)
FDA-approved to treat angina, heart failure with reduced ejection fraction, hypertension, myocardial infarction
 metoprolol succinate (TOPROL-XL)
Disp-30 tablet, R-2

▼ Mineralocorticoid Antagonists (MRA)

▼ eplerenone (Inspira)
FDA-approved to treat hypertension, heart failure after myocardial infarction
 eplerenone (INSPRA) 25 mg tablet
Disp-30 tablet, R-2

▼ spironolactone (Aldactone)
FDA-approved to treat ascites due to cirrhosis, heart failure with reduced ejection fraction, hypertension, primary hyperaldosteronism
 spironolactone (ALDACTONE) 100 mg tablet
Disp-30 tablet, R-2

▼ SGLT-2 Inhibitors

▼ Dapagliflozin (Farxiga)
FDA-approved to treat type 2 diabetes mellitus, heart failure with reduced ejection fraction
 dapagliflozin (FARXIGA) 10 mg tablet
Disp-30 tablet, R-2

▼ Empagliflozin (Jardiance)
FDA-approved to treat type 2 diabetes mellitus
 empagliflozin (JARDIANCE) 10 mg tablet
Disp-30 tablet, R-2

▼ Additional SmartSet Orders

Search
You can search for an order by typing in the header of this section.

Alerts will fire only once per provider, during the first encounter in which a patient is eligible and only when the chart is open to enter orders. This ensures that the alert is displayed at the most relevant places in a provider's workflow and will minimize alert burden. Once a patient is seen by an enrolled provider, they will not generate further alerts, which will ensure that a patient who sees two providers in different arms of the study will not be enrolled twice.

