Should a patient have a documented allergy or contraindication to a particular medication class, this class will not be displayed in the order set for that patient. We will also provide the clinician with the opportunity to dismiss the alert and indicate the reason, including if the patient had any contraindications. Any patient seen by a provider that is randomized to the control study arm will not generate an alert for their provider, but a "silent alert" that registers the patient into the study. Patients will receive care as usual.

Endpoints: The primary outcome for the trial will be the proportion of patients with HfrEF who have an increase in the number of prescribed evidence-based therapies for HfrEF (beta-blockers, ACE-I/ARB/ARNI, MRA, SGLT2i) 30 days post randomization. This endpoint will be based on the prescription of medication rather than filling of the prescription by the patient.

Secondary outcomes will include: percentage of patients prescribed each medication class (i.e. percentage on beta-blockers, percentage on ACE-I/ARB/ARNIs, percentage on SGLT2i, and percentage on MRAs), the percent of filled prescriptions (as assessed by Sure Scripts), medication doses, one-year all-cause mortality, 30-day all-cause hospital admission rate, all-cause 30-day ED visits, and 6 month total healthcare costs. Other data that is present in the EHR that might be related to adverse events such as falls will also be collected. Outcomes will be determined by review of medical, hospital, and billing records.

Secondary analyses will look at outcomes based on insurance coverage, specialty of the provider, and according to prescriptions filled by patients. We will also stratify analyses by provider type (MD vs PA vs NP). Finally, per request of our DSMB, we will collect laboratory values and vital signs as categorical variables to enable simpler detection of safety signals as the data accrues, as well as secondary endpoints at 60 days (to include ED visits, hospitalizations, and all-cause mortality).

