Should provider outreach via email prove difficult, we will use other means to contact eligible clinicians. The first will be via an Epic in basket message, where the informed consent will be copied directly into the body of an Epic message that is then sent to the eligible provider. The provider can then read through the consent and reply back with "Yes I do not consent" or "No I do not consent", without requiring a signature. This response will be documented, and consented providers will then be sent instructions and a link for the REDCap survey.

We will also contact via telephone. Study coordinators will contact eligible providers via phone to describe the study, answer questions, and receive and document verbal consent. Consented providers will then be sent instructions and a link for the REDCap survey.

If/when feasible, study coordinators will also conduct in-person signed consent.

Data for this study (consent and survey only) will be collected, recorded and stored using REDCap. REDCap is a secure, web application designed to support data capture for research studies. It includes features for HIPAA compliance including real-time data entry validation (e.g. for data types and range checks), a full audit trail, user-based privileges, de-identified data export mechanism to statistical packages (SPSS, SAS, Stata and R), and integration with the institutional Active Directory. Access to study data in REDCap will be restricted to the members of the study team with authentication through University NetID credentials. The REDCap@Yale database and web server are housed on secure platforms that are backed up daily. REDCap@Yale meets the security standards for use with high risk data as set forth by the [Yale Information Security Office](#). Electronic data will be kept in password-protected files located within REDCap™. Access to the study's data in REDCap™ will be restricted to the members of the study team by username and password.

Prior and Concomitant Therapy: All therapies are permissible within this protocol.

Blinding of Intervention: Patients will not be informed of their randomization status or participation in this trial as the trial could not be feasibly performed if subjects were told they were enrolled. Provider subjects will, obviously, not be blinded to the intervention as they are receiving the alert and will be consenting to participate in the study. We will engage in both

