- Already receiving each of the four classes of evidence-based HFrEF medical therapy

Providers must be practicing at an outpatient cardiology and internal medicine practices within one of the four teaching hospitals within the Yale New Haven Health System and will be selected for study participation based on the frequency with which they see patients who meet the above criteria, based on a retrospective chart review.

How will eligibility be determined, and by whom?

Eligibility of patients will be assessed automatically by the best practice alert framework directly within Epic and will not involve any human intervention. When a provider opens the order entry screen of the patient's medical record, this build will examine the record for all inclusion and exclusion criteria. Those who meet criteria will be immediately and automatically enrolled and placed into a randomization group based on the randomization status of their current provider at the time of enrollment. Providers will be selected as described above via retrospective chart review by study investigators.

Protection of Human Subjects: Protection of Human Subjects: Modifications Made in Response to Findings from the Electronic Alerts for the recently completed Acute Kidney Injury Amelioration (ELAIA-1) trial: The recently completed ELAIA-1 trial was *negative*. Alerts about acute kidney injury (AKI) did not reduce progression, dialysis initiation or death rates among hospitalized patients with AKI. However, there was a small signal for harm at one non-teaching hospital (Lawrence and Memorial Hospital). *Despite* heart failure being an *entirely* different disease state and the intervention being tested in PROMPT-HF is guideline based whereas ELAIA was not, we are making the following modifications to the study out of an abundance of caution. *These have been made in partnership with the leadership at both Yale School of Medicine/Yale Center for Clinical Investigation (YCCI) and Yale New Haven Hospital: Drs. [name] (YCCI), [name] (YCCI), [name] (YNHS), and [name] (YNHS) who believe that studies of decision support tools continue to pose minimal risk to patients.*

The changes are as follows:

- We will restrict the study only to *teaching* hospitals within the YNHS: Yale New Haven, Greenwich, Bridgeport, Hospital of Saint Raphael
- Our Data Safety Monitoring committee will perform an interim analysis of the data at 25% and 50% enrollment

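### Patients enter the trial only when an unblinded, already randomised provider opens order entry, and the plan has no analysis that would show whether this selects patients differently in the two arms

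*Combined protocol and SAP*

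**What the plan says.** All references are to Section I of the combined protocol and SAP.

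- **Order of events.** Under Randomization, consented providers are allocated to an arm and stay there. Under Subject Recruitment, a patient takes the arm of the provider at the first eligible outpatient visit.
- **Trigger for enrolment.** Under the question on how eligibility is determined, once a provider has opened order entry for a patient, "this build will examine the record for all inclusion and exclusion criteria". Under Subject Recruitment: "Upon opening the patient's medical chart and placing orders, the build will examine the patient record". Neither sentence distinguishes the arms. They differ on whether opening the screen is enough or orders must be placed.
- **Alert display.** Under Intervention, alert-arm providers "will have a best practice alert appear for each of their eligible patients upon opening of the order entry screen", and the alert fires "only when the chart is open to enter orders".
- **Control arm.** Also under Intervention: "Any patient seen by a provider that is randomized to the control study arm will not generate an alert for their provider". A silent alert registers the patient instead. Order entry is not mentioned there.
- **Blinding.** "Provider subjects will, obviously, not be blinded to the intervention".
- **Outcome and analysis.** The primary outcome is the proportion of patients with more prescribed classes at 30 days. The analysis is by intention to treat, with a log-link model for adjusted risk ratios; no covariates are named.

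**The concern.** Membership of the analysed set is decided after randomisation, by an act of someone who knows the allocation. That act lies on the path to the outcome, because a prescription requires order entry. It is also an act the intervention could change. The protocol itself expects repeated exposure to the alert to alter provider behaviour and concedes that alert fatigue may occur.

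Suppose alert-arm providers open order entry less often when they plan no change. That arm then loses patients who would not have had an increase, and its response rate rises with no alert effect. Suppose instead that they open it more often. The arm then gains such patients, and a real effect shrinks.

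Intention to treat repairs neither case, since it protects only patients who were enrolled. The contamination and secular-trend analyses ask whether control providers' behaviour changes, not who is enrolled. The plan has no record of eligible visits without order entry, no comparison of enrolment per provider by arm, and no analysis on all eligible patients.

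**Working it through.** **Inputs from Sample Size Determination:** 50 clusters of 13 per arm (650 per arm), control proportion 0.20, alternative 0.30, intracluster correlation 0.05, two-sided unpooled Z-test, significance level 0.048.

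**Plan's own figure.** Design effect = 1 + (13 − 1) × 0.05 = 1.6. Effective n = 650/1.6 = 406.25 per arm. SE = √[(0.3 × 0.7 + 0.2 × 0.8)/406.25] = 0.0302, so z = 0.10/0.0302 = 3.31. Power is 90.9% at 0.048 and 91.207% at 0.05. The stated 91.207% is reproduced, exactly at 0.05 rather than 0.048. The gap is small and not at issue here.

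**False difference with no alert effect.** The documents do not say how often eligible visits lack order entry, so the following are assumptions. A share of 0.20 of eligible patients would have an increase and always reach order entry. The other 0.80 reach it at rate q, and those who do not are never enrolled. Recruitment continues to 650 per arm. Then

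p = 0.20/(0.20 + 0.80q), and rejection = Φ(d/SE − 1.977) + Φ(−d/SE − 1.977),

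where d is the alert minus control difference and SE is as above with the shifted proportions. Control has q = 0.90, so p = 0.20/0.92 = 21.7%.

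| Alert-arm q | Alert-arm p | d (points) | SE | d/SE | Rejection at 0.048 |
|---|---|---|---|---|---|
| 0.90 | 0.20/0.92 = 21.7% | 0 | 0.0289 | 0 | 4.8% |
| 0.85 | 0.20/0.88 = 22.7% | +1.0 | 0.0292 | 0.34 | 6.1% |
| 0.80 | 0.20/0.84 = 23.8% | +2.1 | 0.0294 | 0.70 | 10.5% |
| 0.70 | 0.20/0.76 = 26.3% | +4.6 | 0.0299 | 1.53 | 32.7% |

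Exchanging the arms' q values reverses the sign of d and leaves the rejection rate unchanged.

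**Opposite direction with a true effect.** Take true rates of 30% and 20%, and let the alert arm gain extra patients with no increase. With 5% extra, its rate is 0.30/1.05 = 28.6% and power is 81%. With 10% extra, it is 0.30/1.10 = 27.3% and power is 68%.

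**Cost of enrolling at check-in instead.** With alert-arm q of 0.80 or 0.70, the unalerted share of that arm is 0.80 × 0.20 = 16% or 0.80 × 0.30 = 24%. If a 10-point effect occurs only in alerted patients, the difference is 8.4 or 7.6 points, and power falls from about 91% to 80% or 72%.

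**The case against.** Four points on the other side carry weight.

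1. **One trigger, not two.** A reader might infer from the control-arm sentence that every control patient seen is registered while the alert arm registers order-entry patients only. The documents do not support that. Both sentences that define enrolment are arm-neutral, and the Intervention text elsewhere uses being seen loosely for any enrolled provider. Read literally, the sentence would also register control patients who fail the ejection fraction and registry criteria. It is an ambiguity to close. This stands.
2. **Avoidance needs anticipation.** The alert appears only after order entry opens, can be dismissed, and does not recur for an enrolled patient. At about 13 patients per provider over an estimated two years, the burden is light. This makes strong avoidance less likely but does not exclude it, since the plan itself expects repeated exposure to change behaviour.
3. **A missed visit is not a lost patient.** Someone without order entry at one visit can enrol at a later one. The formula above treats such patients as lost, and as having no increase, so its figures overstate the effect of deferral alone.
4. **Direction.** A reader might infer that any bias must favour the alert. Nothing in the documents fixes the sign.

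Automated eligibility checking is a weaker defence. It removes discretion over the criteria, not over the act that starts the check.

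**Conclusion.** The structural point holds: enrolment follows randomisation, depends on an unblinded provider opening order entry, and is unmonitored for differences between arms. Bias is possible, not shown. Its size and direction are unknown, because every order-entry rate used above is assumed. Within the range of 85% to 70% in the alert arm against 90% in control, the false difference is +1.0 to +4.6 points, against a planned effect of 10, with rejection of about 6% to 33%. Equal rates give none. The conclusion does not depend on the control-arm wording, because it applies with one common trigger. Nor does it require moving primary enrolment to check-in. That is a debatable trade-off with a real power cost, and it changes the question from the effect of a displayed alert to that of assignment to one. What is missing is a way to see the selection if it occurs.

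**What to change.** 1. State one identical enrolment trigger for both arms, and reconcile the wording under Subject Recruitment, Intervention (alert display, firing rule and silent alert) and the eligibility question, including whether opening the screen suffices or orders must be placed.
2. Keep order-entry enrolment for the primary analysis. In addition, retrieve by EHR query, blind to outcome, each patient's first visit to an enrolled provider at which the criteria were met, whether or not order entry was opened.
3. Report by arm the share of these patients who were enrolled, the enrolment per provider, and baseline balance.
4. Prespecify a sensitivity analysis that repeats the primary model on all these patients, by the arm of the provider at that first eligible visit, with the 30 days counted from that visit.

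The cost is a short amendment, one query of routine records and one extra analysis. The sensitivity estimate will be diluted by alert-arm patients who were never alerted, so it should be read beside the enrolled shares in step 3. Similar shares and balance by arm would be reassuring; a clear difference would call for caution about the primary result.
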